# 20.6 Withdrawal criteria

These processes are to be implemented at both study sites.

Subjects who do not meet the screening criteria will be considered screen failures and will be replaced.

Vestibular Stimulation to Trigger Adip Clinical Trial Project Name	75 of 112		
Clinical Protocol for VeS			
Document Title			
243973(NI)_181094(UCSD USA)	Protocol	01	11
Study Reference Number	Document Type	Document Number	Revision Number

Subjects may withdraw from the investigation for any reason, at any time. Subjects are free to participate or not participate as they wish.

During the course of the study, subjects may be withdrawn from further involvement. Reasons for withdrawal may include:

- Subject removal of consent
- Any adverse event (related or not) that in the opinion of the investigator will endanger the well-being of the subject if they continued in the study.
- Poor compliance with the study requirements (protocol violation)
- Subjects lost to follow-up

All subjects withdrawn from the study due to unexpected device effect, directly related to the clinical investigation, will be followed-up and treated until the effect resolves.

Subjects who are withdrawn will not be replaced. All discontinuations will be documented along with the reason for withdrawal. Reasonable efforts will be made to contact any subject lost to follow-up during the course of the investigation in order to complete assessments and retrieve data. Should a subject be lost to follow-up the data available will be used in the final report, all uses of partial data will be documented. Ethics Committees and regulatory authorities will be notified of withdrawal as required by the regulations.

If possible, when a subject withdraws, or is withdrawn, a final visit should be conducted to allow a withdrawal discussion with the subject. At this visit the study device, iPod and any unused consumables should be collected. Also, at this visit it will be requested in a non-coercive manner if the subject will permit their weight to be taken, and if they are willing to complete the Adverse Event monitoring questionnaire. Moreover, if the subject had reached the point where they were due a follow-up appointment (i.e. at 3 and 6 months), then they be asked, again in a non-coercive manner, whether they are willing to have the scheduled tests and measurements for that appointment. It will though be made clear to the subject that these activities are optional on their part.

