Data will be transferred in an encrypted PDF format. Trial staff will be given direction on how to share the trial data and given access to one specific section of a controlled cloud service which is controlled via role based access. Once they have authenticated with the service and the service verifies that they have the correct role to access the system they will be directed to a single webpage within the application where they will be able to upload the encrypted PDF. This PDF is generated on the fly and is therefore not stored in another location that could become compromised. Generating the PDF on the fly means that the source data is extracted from the database, processed and delivered in the context of a single request. This is an important factor as this means that after the request finishes the data in the PDF will not be held in application memory once the request is finished and the data relating to the request is freed. After the PDF is generated it is delivered to the assigned statistician using TLS 1.2 (a strong protocol), ECDHE\_ECDSA with X25519 (a strong key exchange), and AES\_128\_GCM (a strong cipher). These data will be transferred for each subject when they complete participation in the study. If they complete the study protocol this will be at the six month mark, however, if they drop out early then data accrued up until that point will be sent.

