### 34.1 Statistical Plan

#### Analysis Populations

The Primary Analysis population will be the 200 subjects included in the study. The primary analysis population is defined to include all randomized subjects (i.e. an intention-to-treat population).

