## 7. ANALYSIS POPULATIONS

The efficacy analyses will be performed on the Intention to Treat (ITT) population, which will include all randomized subjects. Subjects in the ITT Population will be classified according to the treatment as randomized.

Similarly, the safety and tolerability analyses will be performed on the Safety Analysis Set (SAS) population, which will include all randomized subjects who received either the VeSTAL or sham control devices (i.e., recorded at least one session of use defined as usage on at least one day).

However, subjects in the Safety Analysis Set will be classified according to the treatment received, which may on occasions differ from that randomized.

Should any major protocol deviations occur on study, the Per Protocol (PP) population will be defined which excludes any subjects who violate the protocol in terms of a major deviation. Of particular attention will be those subjects who are non-compliant with device usage. For example, to be included in the PP population, subjects must use the device for at least an average of three and a half hours a week for at least four of the first 6 months. If the PP population contains less than 95% of the ITT population then efficacy analyses will be repeated on the PP population.

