### 10.2 Premature Withdrawal and Missing Data

All subjects enrolled into the study who meet the requirements for the ITT or Safety Analysis Set population will be included in the final analyses. This will include those subjects who withdrew from the study prematurely or have missing data.

For the large part, subjects will contribute what data they have available without imputation. However, for the primary efficacy endpoint of total body weight loss, three approaches to missing or incomplete data will be taken, under the assumption that the data is missing at random:

- 1. Multiple imputation will be applied by means of a multiple imputation model which is composed of three steps:
  - 1.1. The missing data are imputed multiple times to generate multiple sets of data. The imputed values are predicted total body weight loss values obtained from a linear regression model with observed total body weight loss data as the dependent endpoint, and the same covariates of interest that are used to adjust the primary endpoint (treatment group, gender and baseline weight). By providing 75 imputations per missing value, the variability between imputed values represents the uncertainty over the missing value.
  - 1.2. The 75 complete datasets are analyzed using the planned statistical analysis as per section 12.1.1. The results from the 75 complete datasets are then combined to produce an estimate for the primary endpoint, which reflects the uncertainty due to the missing values.
- 2. Last Observation Carried Forward (LOCF) will be applied for all subjects without data, inclusive of those who have withdrawn from the trial and subjects who have not reached the time point.
- 3. Baseline Observation Carried Forward (BOCF) will be applied for all subjects without data, inclusive of those who have withdrawn from the trial and subjects who have not reached the time point.

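### Participants can be withdrawn for poor compliance with no month-6 weighing planned, and the primary imputation takes no account of why they left

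*Protocol*

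**What the plan says.** **Withdrawal.** Protocol 20.6 states: "During the course of the study, subjects may be withdrawn from further involvement". One listed reason is "Poor compliance with the study requirements (protocol violation". No threshold is given, and Protocol 42.6 leaves it to the Principal Investigator whether a violation leads to withdrawal.

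**What is measured afterwards.** A final visit is held if possible, at which "it will be requested in a non-coercive manner if the subject will permit their weight to be taken". Scheduled tests are offered, again as optional, only "if the subject had reached the point where they were due a follow-up appointment (i.e. at 3 and 6 months". Protocol 31 adds that "if they drop out early then data accrued up until that point will be sent". Efforts to retrieve data are described only for participants lost to follow-up.

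**Analysis.** The primary population in Protocol 34.1 is "defined to include all randomized subjects (i.e. an intention-to-treat population", and SAP 7 agrees: "The efficacy analyses will be performed on the Intention to Treat (ITT) population, which will include all randomized subjects". SAP 10.2 imputes missing weight loss under a missing-at-random assumption, using "the same covariates of interest that are used to adjust the primary endpoint (treatment group, gender and baseline weight". Each time point has its own imputation model. Month-3 weight, the withdrawal weight, device use and the reason for leaving therefore play no part in the month-6 imputation. (Protocol 34.1 also lists age and study site as predictors, but none of these four items.)

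**Responder endpoint.** Under SAP 10.2 only participants with missing data who left because of adverse events or a medication change are set to non-responder. All others with missing data, poor compliers included, are classified by their imputed weight.

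**The concern.** The participant stays in the ITT set, but the outcome is replaced by a draw from the distribution of observed participants in the same arm with the same gender and baseline weight. That is unbiased only if poor compliers who are removed resemble those who remain. There is reason to doubt it: SAP 13 (item 2) itself says that a participant may stop because the treatment seems not to work.

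If removed poor compliers do worse, both US co-primary criteria are exposed. The responder criterion is the more exposed because it looks only at the active arm, so no sham-arm error can offset it. The data are lost through a protocol rule, not through participants' refusal, and the month-6 visit at which they could be collected already exists.

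**Working it through.** **Inputs.** From SAP 5 and Protocol 34.3: active mean 6.6%, sham mean 3.1%, SD 3.9%, correlation of 0.4 in size between baseline weight and loss, 180 evaluable 1:1, drop-out 10%. From Protocol 18.1: margin 2 points, one-sided 2.5%, and a 50% responder threshold. **Assumptions** (not in the documents): a fraction f of 5% to 10% of the active arm is withdrawn for poor compliance, and these participants lose the sham mean. The upper end equals the plan's drop-out allowance for all causes.

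**The plan's own figure.** 180 / 0.90 = 200, which reproduces the recruitment target.

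**1. Inflation of the mean difference at planning values.** Bias = f × (6.6 − 3.1).
- f = 5%: 0.05 × 3.5 = 0.175 points
- f = 10%: 0.10 × 3.5 = 0.35 points

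**2. Responder rate.** With normal outcomes, P(loss ≥ 5%) is Φ((6.6 − 5)/3.9) = 65.9% at the active mean and Φ((3.1 − 5)/3.9) = 31.3% at the sham mean. The true active-arm rate is then:
- f = 5%: 0.95 × 65.9 + 0.05 × 31.3 = 64.2%
- f = 10%: 0.90 × 65.9 + 0.10 × 31.3 = 62.5%

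Multiple imputation (MI) returns about 65.9% in both cases.

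**3. Error rate at the 2-point margin.** Here the true ITT difference is 2. If withdrawn active participants lose the sham mean, the rest must differ from sham by 2/(1 − f), so the bias is 2f/(1 − f). The adjusted SD is 3.9 × √(1 − 0.4²) = 3.574, and SE = 3.574 × √(2/90) = 0.533.
- f = 5%: bias 0.105; 1 − Φ(1.96 − 0.105/0.533) = 3.9%
- f = 10%: bias 0.222; 1 − Φ(1.96 − 0.222/0.533) = 6.1%

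**4. Simulation.** The settings were 100 per arm, 10% missing in each arm, predictors arm and baseline weight (gender omitted), 20 imputations instead of the SAP's 75, and 1,500 runs. The responder test used the median count over imputations. Withdrawn participants in both arms lose the sham mean.

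| | MI | Real month-6 weights |
|---|---|---|
| Mean difference, planning values | 3.48 | 3.12 |
| Mean criterion met | 78% | 59% |
| Responder criterion met | 87% | 65% |
| Mean criterion met, true difference 2 | 6.5% | 2.3% |

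**5. Range over other outcomes after withdrawal.** If removed poor compliers resemble the observed participants, the bias is zero. If withdrawn participants in both arms lose nothing (f = 10%), bias at planning values is 0.1 × 6.6 − 0.1 × 3.1 = 0.35 points: the sham arm cancels 0.31 of 0.66. Simulated error at the margin was then 5.5%. If active withdrawals lose nothing while sham withdrawals are typical, bias at planning values is 0.66 points and the simulated error about 16%. That last case is extreme and the conclusion does not rest on it.

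**The case against.** **Supportive analyses exist.** SAP 10.2 and 12.1.2 plan last and baseline observation carried forward (LOCF, BOCF), and for the responder endpoint a best case, a worst case and, if those two conflict, a tipping-point analysis. SAP 12.1 says supportive results are considered together with the primary result. A reader might infer that these add nothing because none recovers the month-6 weight. That goes too far. With 10% withdrawn per arm at the sham mean, the true ITT difference is 0.9 × 6.6 + 0.1 × 3.1 − 3.1 = 3.15, and BOCF gives 0.9 × 6.6 − 0.9 × 3.1 = 3.15. If only the active arm loses people, BOCF gives 0.9 × 6.6 − 3.1 = 2.84, which counts against the device. What stands of the concern is that MI is primary, no rule says what follows if the supportive results disagree, and the worst-case and tipping-point analyses cover only the responder endpoint.

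**Non-compliers are mostly expected to stay.** Withdrawal is optional. Protocol 11.2 answers low use with contact and encouragement, SAP 12.3 summarises month-6 weight loss in low adherers, and SAP 7 defines a per-protocol set to exclude them. It is therefore tempting, but wrong, to say that the imputation draws from compliant completers: it draws from all observed participants in the arm, low adherers included. This weakens the bias and does not remove it. It also shows that the analysis has no need for compliance withdrawals.

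**Both arms are affected.** The requirements include diet and mentoring, which both arms share, so sham poor compliers may also be imputed too favourably. This stands for the mean difference, not for the single-arm responder criterion.

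**ITT is kept.** A reader might infer that the plan contradicts its ITT promise. It does not: Protocol 33 and SAP 10.2 keep withdrawn participants in the analysis. The weakness is in how their outcome is filled in.

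**Conclusion.** The path to bias is real and no other section closes it: withdrawal for poor compliance is allowed, no month-6 weight is planned afterwards, and the primary analysis fills the gap without using anything that marks the participant as a poor complier. The missing weighing is inferred from the absence of any provision, since the protocol does not forbid it.

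With 5% to 10% of the active arm withdrawn this way and losing the sham mean, the size is 0.18 to 0.35 points on the difference, a responder rate of about 66% instead of 62% to 64%, and a one-sided error on the mean criterion of about 4% to 6% instead of 2.5%. US success also needs the responder criterion, so this last figure is not the error rate of the whole claim.

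A reader might infer an error rate up to nearly 10% by applying the 0.35-point inflation at the margin. That combines a true difference of 2 with a gap of 3.5 between imputed and true values, and both cannot hold under these assumptions. Nor do the documents show that the data are missing not at random, or how often such withdrawals occur. The point is a well-founded risk of modest size with a cheap remedy.

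**What to change.** In Protocol 20.6, separate stopping device use from leaving the study. Remove poor compliance as a reason for ending study follow-up, leaving any decision about stopping the device as it is. Invite every randomised participant who has not withdrawn consent to the scheduled month-6 weighing, whatever their device use. The protocol's separate rule on pregnancy is outside this point.

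In SAP 10.2, state that an observed month-6 weight is used in the ITT analysis regardless of device use, so that MI applies only to weights still missing.

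The cost is protocol wording and some contact effort; the visit already exists. The downside is that some retrieved weights will be off-device, which suits an ITT analysis but should be reported. The change helps only participants whose month-6 visit is still ahead.

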## 21. Investigation Procedures

## 21.1 Informed Consent

In order to facilitate the identification of prospective research participants who meet the eligibility criteria for enrollment review it is proposed that pre-screening by telephone take place. In order to allow this to take place over the telephone it is requested that a waiver of consent documentation is allowed.

As this pre-screening process will collect identifiable information that includes Protected Health Information (PHI) prior to obtaining consent to participate in the study, we wish to request a waiver of individual HIPAA authorization. Below we describe how each of the following criteria for granting the waiver will be satisfied:

a) Why the disclosure of PHI involves no more than minimal risk.

This process is considered minimal risk to the potential subjects as all data gathered via this process will be treated in the same confidential manner as data gathered at any other part of the study. Moreover, all data for subjects deemed ineligible to participate will be destroyed at the end of the phone call to pre-screen them.

b) Why granting the waiver will not adversely affect privacy rights and welfare of the individuals whose records will be used.

It is not believed that this process will adversely affect the privacy rights and welfare of potential subjects that are pre-screened as the telephone script still includes the Elements of Consent. Potential subjects are thus

Vestibular Stimulation to Trigger Adipose Loss (VeSTAL) Clinical Trial				77 of 112
Clinical Protocol for VeSTAL				
243973(N USA)	II)_181094(UCSD	Protocol	01	11
Study Reference	e Number	Document Type	Document Number	Revision Number

requested to give verbal consent to undergo the pre-screening process. Other than the data provided over the phone by potential subjects undergoing the pre-screening process no hospital records or other PHI will be accessed as part of the telephone pre-screening process.

c) Why the project could not practically be conducted without a waiver.

The pre-screening process takes place over the phone it is not possible to obtain signed consent.

Without the waivers of documented consent and individual HIPAA authorization in place the recruitment process would be much more cumbersome, a lot less practical and potentially significantly inconvenient for the potential subjects, as there are multiple inclusion and exclusion criteria. Thus, many potential subjects would attend in person at Clinical Site despite being clearly ineligible to participate in the study.

d) Why the project could not practically be conducted without the use of PHI.

There are over 30 inclusion and exclusion criteria, many of which pertain to aspects of PHI, and several of which relate to various relatively common health conditions and medications. Thus, without the use of PHI it would be impossible to inadequately screen potential subjects properly, and many would attend in person at the Clinical Site despite being obviously ineligible to participate in the study.

e) An adequate plan to protect identifiers from improper use and disclosure.

No identifiers will be attached to the pre-screening documentation, and no identifiers will be collected during the pre-screening process. At the end of the phone call to pre-screen subjects it will be determined whether the subject appears likely to be eligible or ineligible to pass the study's screening process. Eligible subjects will be invited to attend the Clinical Site to be consented and enrolled into the study. Once this determination regarding eligibility is made the pre-screening questionnaires will be destroyed for all subjects.

A separate document detailing the potential subjects who have been contacted via the pre-screening process will be kept in a locked data cabinet in the Clinical Site. (If this information is stored on a computer, then it will be on a Clinical Site computer assigned to study staff by the Clinical Site for research purposes, and it will require a password for access, which only personnel directly involved in the study will have.) No PHI will be on this document. Rather, all that will be recorded is whether the potential subject was found eligible or ineligible

Vestibular Stimulation to Trigger Adipose Loss (VeSTAL) Clinical Trial				78 of 112
Clinical Protocol for VeSTAL				
	43973(NI)_181094(UCSD JSA)	Protocol	01	11
	tudy Reference Number	Document Type	Document Number	Revision Number

via the pre-screening process. (It is necessary to keep a record of the names of the potential subjects found ineligible to proceed to avoid accidentally contacting the same person twice during the recruitment period).

Access to these data in any format will only be available for study staff on the protocol. All data gathered via this process will be treated in the same confidential manner as data gathered at any other part of the study. Once recruitment to the study is complete (i.e. 200 subjects have successfully passed the screening process after giving informed consent) then this list of subjects who underwent the pre-screening process will also be destroyed.

f) An adequate plan for destroying the identifiers at the earliest opportunity, or justification for retaining identifiers.

No identifiers will be collected as part of the pre-screening process and no identifiers will be marked on the prescreening documentation, which will be destroyed at the end of the pre-screening call after determining likely eligibility. Once recruitment to the study is complete (i.e. 200 subjects have successfully passed the screening process after giving informed consent) then the list of subjects who underwent the pre-screening process will also be destroyed. (See Section (e) above).

g) Written assurance that the PHI will not be re-used or disclosed for other purposes.

We provide assurance that the protected health information (PHI) will not be re-used or disclosed for other purposes except as required by law, or for authorized oversight of this research study.

h) Whether it is appropriate to provide the subjects with additional pertinent information after participation and, if so, how this will be accomplished.

As identifiers will not be collected during the pre-screening it is not appropriate for all the potential subjects prescreened to be provided with additional information. Those subjects judged eligible to proceed on the basis of the phone pre-screening will be invited to a face-to-face meeting at the clinical site. There they will be provided with a copy of the Informed Consent Form, which the research coordinator will then talk through with them.

# 21.2 Obtaining Informed Consent

Informed consent will be taken by clinical trial coordinators at the clinical site. This will be done in a private room at the clinical site in a manner that is non-coercive and using language that is understandable to the

Vestibular Stimulation to Trigger Adipe Clinical Trial Project Name	79 of 112		
Clinical Protocol for VeS			
243973(NI)_181094(UCSD USA) Study Reference Number	Protocol Document Type	01 Document Number	11 Revision Number

potential participants. No exculpatory language will be used, and the participants will not be asked to waive any of their legal rights. The subjects will be informed about the purpose and the duration of the current study, and the Informed Consent Form will be talked through with the subject. The procedures and objectives will be described. As will all investigations, potential discomforts, risks and benefits of participation. Sufficient time will be given to subjects to decide whether they wish to participate. Informed consent will be obtained, once the subject has been informed and wants to participate in this investigation, using the attached informed consent form.

In all cases of informed consent detailed below, the principal investigator (or approved designee) will sign the same consent form, on the same occasion as the subject. Three copies of the consent form will be made at UCSD and UU sites. The original copy of the signed consent documents will be kept in the Investigator site file at the investigation site. A copy will then be filed in the subject's medical notes at the clinical site, and a further copied provided to the subject. Where sites utilize electronic medical notes, a note of the patient's participation in this clinical investigation should also be made in the system. Two copies of the consent form will be made at the TDE site. The original copy of the signed consent documents will be kept in the Investigator site file at the investigation site and a scanned copy will be provided to the subject. Written informed consent from the subject must be obtained before any investigation related procedures (including screening procedures) are performed.

The investigator or another member of the investigative team should appropriately address all and any queries that a patient may have regarding the clinical investigation.

The investigator will return to the subject after sufficient time has elapsed and provide a recap of the clinical investigation. The approved consent form will then be provided to the subject in order to obtain written consent. In order that consent provided by the patient is voluntary and fully informed the subject should:

- Understand the purpose and nature of the investigation
- Understand what the investigation involves, its benefits (or lack of benefits), risks and burdens
- Understand the alternatives to taking part
- Be able to retain the information long enough to make an effective decision
- Be able to make a free choice and free form coercion
- Be capable of making this particular decision at the time it needs to be made.

Vestibular Stimulation to Trigger Adip Clinical Trial Project Name	80 of 112		
Clinical Protocol for VeS			
243973(NI)_181094(UCSD USA) Study Reference Number		01	11 Revision Number

